4. SUBJECT DISPOSITION

4.1. Subject Enrollment and Disposition

4.1.1. Subject Enrollment

All summaries on subject enrollment have been performed as part of the Week 48 analysis, and will not be repeated in the final analysis.

4.1.2. Subject Disposition

The summary of subject disposition will be provided by treatment group and overall using the All Randomized Analysis Set for all B/F/TAF analysis (Appendix 2; [Appendix Table 1](#)). This summary will include the number of subjects who were randomized, randomized but not treated, randomized and treated, subjects who prematurely discontinued study treatment in the randomized phase, subjects who completed the randomized phase but not entered the extension phase, subjects who entered the extension phase, who received B/F/TAF in either the randomized or extension phase (ie, All B/F/TAF Analysis Set).

In addition, the number and percentage of the subjects from the All B/F/TAF Analysis Set in the following categories will be summarized:

- Completed B/F/TAF
- Prematurely discontinuing B/F/TAF (with summary of reasons for discontinuing study treatment)
- Completed study
- Prematurely discontinuing (with summary of reasons for discontinuing study)

The denominator for the percentages of subjects in each category will be the number of subjects in the All B/F/TAF Analysis Set.

No inferential statistics will be generated. A data listing of reasons for premature study drug/study discontinuation from both phases will be provided.

4.2. Extent of Study Drug Exposure and Adherence

4.2.1. Duration of Exposure to B/F/TAF

Duration of exposure to B/F/TAF is defined as (the last dose date of B/F/TAF – the first dose date of B/F/TAF + 1), regardless of temporary interruptions in study drug administration, and will be expressed in weeks using up to 1 decimal place (eg, 4.5 weeks).

Duration of exposure to B/F/TAF will be summarized using descriptive statistics (n, mean, SD, median, Q1, Q3, minimum, and maximum) and as the number and percentage of subjects exposed for specified periods, eg, ≥ 4 weeks (28 days), ≥ 8 weeks (56 days), ≥ 12 weeks (84 days), ≥ 24 weeks (168 days), ≥ 36 weeks (252 days), ≥ 48 weeks (336 days), ≥ 60 weeks [420 days], ≥ 72 weeks [504 days], ≥ 84 weeks [588 days], ≥ 96 weeks [672 days], ≥ 108 weeks [756 days], ≥ 120 weeks [840 days], etc.

Summaries will be provided by treatment group for subjects in the All B/F/TAF Analysis Set. No inferential statistics will be provided.

Time to premature discontinuation of study drug will be analyzed using the Kaplan-Meier method by treatment group based on the All B/F/TAF Analysis Set. No statistical comparisons will be made for the all B/F/TAF analysis. Subjects who completed study drug will be censored at the last dose date of the study.

4.2.2. Adherence to Study Drug Regimen

Study drug regimen adherence will be computed based on pill counts for B/F/TAF only. The numbers of pills of B/F/TAF dispensed and returned are captured on Study Drug Accountability eCRF. Adherence will be summarized for B/F/TAF during the entire study (including both the randomized and extension phase if applicable).

Adherence (%) of B/F/TAF will be calculated as follows:

$$\begin{aligned} \text{Adherence}(\%) &= 100 \times \frac{\text{Number of pills taken}}{\text{Number of pills prescribed}} \\ &= 100 \times \frac{\text{Sum of No. of pills taken at each dispensing period [1]}}{\text{Sum of No. of pills prescribed at each dispensing period [2]}} \end{aligned}$$

[1] Number of pills taken at a distinct dispensing period for a study drug is calculated as the minimum of (a) the daily number of pills prescribed for the study drug multiplied by the duration of treatment at the dispensing period of the same dispensing date, and (b) the number of pills taken for the study drug (number of pills dispensed minus the number of pills returned). Total number of pills taken is determined by summing the number of pills from all evaluable dispensing periods.

[2] Number of pills prescribed at a distinct dispensing period for a study drug is calculated as the daily number of pills prescribed for the study drug multiplied by the duration of treatment at the dispensing period of the same dispensing date. Total number of pills prescribed is determined by summing the number of pills prescribed from all evaluable dispensing periods.

The duration of treatment at a dispensing period for a study drug is calculated as the minimum of (a) the last returned date of the same dispensing period for the study drug, (b) date of premature discontinuation of the study drug, and (c) next pill dispensing date of the study drug, minus dispensing date of the study drug.

The next pill dispensing date is the following dispensing date of the study drug regardless of the bottle return date.

For a record where the number of pills returned was missing (with “Yes” answered for “Was Bottle returned?” question), it is assumed the number of pills returned was zero. If the number of pills dispensed was missing or any study drug bottle was not returned or the bottle return status was unknown, all records in that dispensing period for that study drug will be excluded from both denominator and numerator calculation.

Adherence to the study drug B/F/TAF will be calculated for each subject in the All B/F/TAF Analysis Set for the entire B/F/TAF dosing period up to the date of permanent discontinuation of B/F/TAF for subjects who prematurely discontinued B/F/TAF or using all data available for subjects completing B/F/TAF.

Descriptive statistics for overall adherence for B/F/TAF (n, mean, SD, median, Q1, Q3, minimum, and maximum) along with the number and percentage of subjects belonging to adherence categories (eg, < 80%, ≥ 80% to < 90%, ≥ 90% to < 95%, ≥ 95%) will be provided by treatment group for subjects who return at least 1 bottle and have calculable adherence during the study in the All B/F/TAF Analysis Set. No inferential statistics will be provided.

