## **5.5. Accountability for Investigational Medicinal Product (IMP)**

The investigator is responsible for ensuring adequate accountability of all used and unused IMP. This includes acknowledgement of receipt of each shipment of IMP (quantity and condition). All used and unused IMP dispensed to subjects must be returned to the site.

Study Drug accountability records will be provided to each study site to:

- Record the date received and quantity of IMP kits
- Record the date, subject number, subject initials, the IMP kit number dispensed
- Record the date, quantity of used and unused IMP returned, along with the initials of the person recording the information

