## 6.6.2. 30 Day Follow Up

Subjects who complete the study through the Week 48 visit and do not continue participation in the study will be required to return to the clinic 30 days after the completion of study drug for the 30-Day Follow-Up Visit.

Subjects who prematurely discontinue study drug and refuse to continue in the study through the Week 48 visit will be asked to return to the clinic 30 days after the completion of the Early Study Drugs Discontinuation Visit for the 30-Day Follow-Up Visit.

**Those subjects who prematurely discontinue study drug and continue in the study through at least one subsequent visit after the Early Study Drug Discontinuation Visit will not be required to complete the 30-Day Follow-Up Visit.**

Subjects who participate post Week 48 will complete a 30-Day Follow-Up Visit 30 days after last dose of study drug.

For the purpose of scheduling a 30-Day Follow-Up Visit, a  $\pm$  6 days window may be used. The following evaluations are to be completed at the 30-Day Follow-Up Visit:

- Review of AEs and changes in concomitant medications
- Symptom-directed physical examination
- Vital signs measurement (blood pressure, pulse, respiration rate, and temperature), including weight
- Urine collection for the following laboratory procedures:
  - Urinalysis
  - Urine pregnancy test (women of childbearing potential only); positive urine pregnancy tests will be confirmed with a serum test.
- Blood sample collection for the following laboratory analyses:
  - Chemistry profile: alkaline phosphatase, AST, ALT, GGT, total bilirubin, direct and indirect bilirubin, total protein, albumin, bicarbonate, BUN, calcium, chloride, creatinine, glucose, phosphorus, magnesium, potassium, sodium, uric acid, and amylase (reflex lipase testing is performed in subjects with total amylase  $> 1.5 \times$  ULN).
  - Estimated glomerular filtration rate according to the Cockcroft-Gault formula
  - Hematology profile: complete blood count (CBC) with differential and platelet count
  - Plasma HIV-1 RNA
  - CD4+ cell count

At the 30-Day Follow-Up Visit, any evaluations showing abnormal results believed to be a reasonable possibility of a causal relationship with the study drugs will be repeated weekly (or as often as deemed prudent by the Investigator) until the abnormality is resolved, returns to baseline, or is otherwise explained.

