1.2. Study Design

Design Configuration and Subject Population

GS-US-380-1961 is a randomized, open-label, multicenter, active-controlled study to evaluate the safety and efficacy of switching to an FDC of B/F/TAF in HIV-1 infected women who are virologically suppressed (HIV-1 RNA < 50 copies/mL) on a regimen consisting of E/C/F/TAF, E/C/F/TDF, or ATV+RTV+FTC/TDF for ≥ 12 consecutive weeks prior to screening.

All subjects will be HIV-1 infected women drawn from pre-defined Gilead Sciences (Gilead) clinical studies and must be virologically suppressed. Women in Study GS-US-236-0128 who completed the Week 48 open-label extension (OLE) visit or any post Week 48 OLE visits, women in Study GS-US-292-0109 who completed the Week 96 visit or any post Week 96 visits, or women in Studies GS-US-292-0104 or GS-US-292-0111 who completed the Week 144 visit or any post Week 144 visits may be eligible to enroll in Study GS-US-380-1961.

Treatment Groups

Subjects who provide written consent and meet all eligibility criteria will be randomized in a 1:1 ratio to receive open-label medication as follows:

Treatment Group 1: FDC of BIC 50 mg/FTC 200 mg/TAF 25 mg (B/F/TAF) administered orally, once daily, without regard to food (approximately n = 235)

Treatment Group 2: Stay on baseline regimen (SBR), including E/C/F/TAF, E/C/F/TDF, or ATV+RTV+FTC/TDF administered orally, once daily, with food (approximately n = 235)

Key Eligibility Criteria

Medically stable HIV-1 infected women who meet the following criteria:

- Currently on a stable antiretroviral regimen consisting of E/C/F/TAF, E/C/F/TDF, or ATV+RTV+FTC/TDF continuously for ≥ 12 consecutive weeks preceding the screening visit
- Documented plasma HIV-1 RNA levels < 50 copies/mL for ≥ 12 weeks preceding the Screening visit. After reaching HIV-1 RNA < 50 copies/mL, single values of HIV-1 RNA ≥ 50 copies/mL followed by re-suppression to < 50 copies/mL is allowed
- HIV-1 RNA < 50 copies/mL at screening
- Estimated glomerular filtration rate (eGFR) ≥ 50 mL/min according to the Cockcroft-Gault (C-G) formula at the screening visit

Study Periods / Phases

Subjects will be treated for at least 48 weeks. At the Week 48 Visit, subjects in a country where B/F/TAF FDC is not available will be given the option to receive B/F/TAF FDC for an additional 48 weeks, or until the product becomes accessible to subjects through an access program, or until Gilead elects to discontinue the study in that country, whichever occurs first.

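### SAP 4.2.2 has no last-dose cap on a completer's final dispensing period, so a bottle returned late counts undosed days as missed pills

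*SAP*

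**What the plan says.** In SAP 4.2.2, adherence is the sum of pills taken over the sum of pills prescribed, across dispensing periods.

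- **Pills prescribed in a period:** "the daily number of pills prescribed for the study drug multiplied by the duration of treatment at the dispensing period". B/F/TAF is "administered orally, once daily, without regard to food" (SAP 1.2), so the daily number is 1.
- **Pills taken in a period:** the smaller of that same product and "number of pills dispensed minus the number of pills returned".
- **Duration of a period:** it "is calculated as the minimum of (a) the last returned date of the same dispensing period for the study drug", with the other limbs given as "b) date of premature discontinuation of the study drug, and (c) next pill dispensing date of the study drug, minus dispensing date".
- **Unreturned bottles:** if any bottle was not returned, or its return status is unknown, the whole dispensing period leaves both numerator and denominator.
- **Cut-off:** a later sentence in 4.2.2 stops the calculation at permanent discontinuation for women who stop early, "or using all data available for subjects completing B/F/TAF".

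SAP 3.8.1 defines a Last Dose Date for completers as well as for early stoppers, and SAP 4.2.1 uses it for duration of exposure. The adherence formula does not.

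On bottle return, Protocol 5.5 states: "All used and unused IMP dispensed to subjects must be returned to the site". Protocol 5.3 asks subjects to bring all study medication to every clinic visit. On the follow-up visit, Protocol 6.6.2 states: "Subjects who participate post Week 48 will complete a 30-Day Follow-Up Visit 30 days after last dose of study drug", with a window of ±6 days. The procedures tables (Protocol Appendix 2, SAP Appendix 1) mark drug accountability at Weeks 4 to 48, at post-Week 48 visits and at the early discontinuation visit. The 30-Day Follow-Up cell is blank.

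**The concern.** The denominator should count days on which a pill was due. For a completer's final period it counts days until the bottle came back. When return follows the last dose by more than a day, the denominator grows while dispensed minus returned stays the same.

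The rule also treats three women with identical pill-taking differently. An early stopper who returns her bottle late is capped by limb (b). A woman who never returns it has the period dropped. A completer who returns it late is charged with pills she was never meant to take.

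What is at stake is the descriptive adherence summary: the group statistics and the counts in the bands < 80%, 80 to < 90%, 90 to < 95% and ≥ 95%. The effect on an affected woman is larger the shorter her B/F/TAF exposure. Exposure is planned to be at most about 48 weeks for SBR to B/F/TAF and about 96 weeks for women randomized to B/F/TAF who extend.

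**Working it through.** The plan states no adherence figure to reproduce, so the check applies the SAP 4.2.2 formula to a simple case.

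**Which limb governs.** Every period except the last is capped by the next dispensing date. In the last period limb (c) is empty, and for a completer limb (b) is empty too. Only limb (a), the return date, remains.

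**Inputs**
- Daily pills: 1 (SAP 1.2).
- d: days on B/F/TAF, every pill taken. The values 84, 168, 336 and 672 days (12, 24, 48 and 96 weeks) are illustrative.
- L: undosed days between last dose and logged return. The illustrative value is 30, with 24 and 36 from the ±6-day window of Protocol 6.6.2.
- All leftover tablets come back and are counted, so dispensed minus returned equals d.

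**Formula.** Pills taken = d. Pills prescribed = d + L. Reported adherence = d/(d + L); the true value is 100%.

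| d (days) | L = 24 | L = 30 | L = 36 | Band at L = 30 |
|---|---|---|---|---|
| 84 | 84/108 = 77.8% | 84/114 = 73.7% | 84/120 = 70.0% | < 80% |
| 168 | 168/192 = 87.5% | 168/198 = 84.8% | 168/204 = 82.4% | 80 to < 90% |
| 336 | 336/360 = 93.3% | 336/366 = 91.8% | 336/372 = 90.3% | 90 to < 95% |
| 672 | 672/696 = 96.6% | 672/702 = 95.7% | 672/708 = 94.9% | ≥ 95% |

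**Where the bands break, L = 30.** Reported adherence is below 95% when d < 0.95 × 30/0.05 = 570 days, below 90% when d < 0.90 × 30/0.10 = 270 days, and below 80% when d < 0.80 × 30/0.20 = 120 days.

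**Comparison cases.** With L = 0 the formula gives 100% at every d. An early stopper with the same pills and the same 30-day late return also scores 100%, because limb (b) ends her period at discontinuation.

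**Day counting.** The duration is a difference of dates with no day added. A woman who takes her first tablet on the dispensing day and returns the bottle 30 calendar days after her last dose is therefore charged 29 undosed days, not 30. That gives 84/113 = 74.3% and 168/197 = 85.3%. The bands do not change.

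**The case against.** The case against reach is strong, and most of it stands.

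- **The 30-Day Follow-Up is not an accountability visit.** The procedures tables leave that cell blank and the evaluations in Protocol 6.6.2 omit it. Protocol 5.3 leaves return at that visit possible, but it is an exception to the planned flow.
- **Forgotten bottles are partly handled.** A bottle that never comes back removes its period from the calculation. The error needs a bottle missed at the last accountability visit, later returned, and logged with the later date.
- **Stopping between visits depends on coding.** In the extension, B/F/TAF may end when the product becomes accessible or the sponsor closes the study in a country, which need not fall on a 12-weekly visit. Protocol 6.6.1 defines the early discontinuation visit only for stopping before Week 48, so the next visit could be the 30-Day Follow-Up. Whether such a woman counts as a completer depends on the Study Drug Completion eCRF, which is not among the documents. If she is coded as premature, limb (b) caps her.
- **No inference rests on it.** SAP 4.2.2 plans no inferential statistics, and the final analysis has no per-protocol set.

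One argument does not succeed. The cut-off sentence in SAP 4.2.2 speaks of the whole B/F/TAF dosing period, which might be read as limiting the count to dosing days. It then truncates only early stoppers and does not alter the duration formula.

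A reader might infer that completers' adherence is biased downward as a class, that the B/F/TAF and SBR to B/F/TAF columns must differ for this reason, or that a given share of women drops out of the ≥ 95% band. The documents support none of these: on-time returns carry no error, and no rate of late return is given or derivable.

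**Conclusion.** The drafting gap is real and narrow. As written, the rule gives a wrong value for a completer whose last bottle is returned and logged more than a day after her last dose, and a correct value for one who returns it at her last on-drug visit. Only the final dispensing period is affected, and the error always understates adherence.

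For an affected, perfectly adherent woman with 30 undosed days, the shortfall is 26.3 points at 12 weeks, 15.2 at 24, 8.2 at 48 and 4.3 at 96 (100 minus the tabulated values). These sizes assume that lag, full pill-taking and a complete tablet count. The effect on group means and band counts cannot be stated, because the number of late returns is unknown. No efficacy conclusion changes. This is a cheap improvement to a descriptive table.

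**What to change.** In SAP 4.2.2, keep limbs (a) to (c) and add limb (d): for subjects who completed B/F/TAF, the Last Dose Date of B/F/TAF from Section 3.8.1 plus 1 day, so that the last dosing day counts. Align the sentence on using all available data for completers. Apply limb (d) only when the last dose date is complete. Appendix 5 imputes a partial date from day 15, and an imputed cap could cut off real dosing days and hide missed pills.

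With limb (d), the perfectly adherent completer scores 84/84, 168/168, 336/336 or 672/672, which is 100% whatever the return date, and values for on-time returns do not change.

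The cost is a line of wording and a line of code, using a variable already derived for exposure. SAP Section 1 provides for changes after finalization to be documented in the clinical study report. The downsides are that completers' adherence then relies on the recorded last dose date, and that subjects with imputed dates stay uncapped.

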4.3. Protocol Deviations

A listing will be provided for all randomized subjects who violated at least 1 inclusion or exclusion criterion. The listing will include the criteria not met. A listing of subjects who received the wrong study drug will also be provided.

5. BASELINE CHARACTERISTICS

5.1. Demographics and Baseline Characteristics

Subject demographic data (eg, age, sex, race, and ethnicity) and baseline characteristics (eg, body weight, height, and body mass index [BMI]) will be summarized by treatment group and overall using descriptive statistics (n, mean, SD, median, Q1, Q3, minimum and maximum) for continuous data and by the number and percentage of subjects for categorical data. Age is calculated as age in years at first dose of B/F/TAF. The summaries of demographic data and baseline subject characteristics will be provided using the All B/F/TAF Analysis Set.

5.2. Baseline Disease Characteristics

The following baseline disease characteristics will be summarized:

- HIV-1 RNA categories (copies/mL): (a) < 50, (b) ≥ 50
- CD4+ cell count (/μL)
- CD4+ cell count categories (/μL): (a) < 50, (b) ≥ 50 to < 200, (c) ≥ 200 to < 350, (d) ≥ 350 to < 500, and (e) ≥ 500
- CD4 percentage (%)
- Mode of infection (HIV risk factors)
- HIV disease status
- eGFR_{CG} (mL/min)

No statistical comparisons will be made for the all B/F/TAF analysis.

5.3. Medical History

Medical history data were presented in the original studies from which subjects were rolled over. Thus, medical history data will not be summarized in this study.

6. EFFICACY ANALYSES

6.1. Definition of Efficacy Endpoints

6.1.1. Primary Efficacy Endpoint

The primary efficacy endpoint is the proportion of subjects with virologic failure (HIV-1 RNA ≥ 50 copies/mL) at Week 48 as defined by the modified FDA snapshot algorithm.

The analyses of the primary efficacy endpoint were performed in the Week 48 interim analyses, and will not be repeated in the final analysis.

6.1.2. Secondary Efficacy Endpoints

The secondary efficacy endpoints include:

- The proportion of subjects with HIV-1 RNA < 50 copies/mL at Week 48 as determined by the US FDA-defined snapshot algorithm
- The change from baseline in CD4+ cell count at Week 48

6.1.3. Tertiary Efficacy Endpoints

CCI

[REDACTED]

[REDACTED]

[REDACTED]

6.2. Analysis of the Efficacy Endpoints

Analyses of the proportions of subjects determined by the US FDA-defined Snapshot Algorithm (the primary efficacy endpoint at Week 48 and part of the secondary CCI efficacy endpoints) were performed in the Week 48 interim analyses and will not be repeated in this final analysis.

6.2.1. Analysis of CD4 Cell Count and CD4%

CD4 cell count and CD4% will be summarized using observed, on-treatment data (ie, data collected up to 1 day after the last dose date of B/F/TAF) for subjects in the All B/F/TAF Analysis Set.

The changes from baseline in CD4 cell count and CD4% at each visit will be summarized by treatment group using descriptive statistics based on observed data (ie, missing will be excluded) using the All B/F/TAF Analysis Set.

The mean and 95% CI of change from baseline in CD4 cell count over time will be plotted using observed data for the All B/F/TAF Analysis Set.

6.2.2. Analysis of the Proportion of Subjects with HIV-1 RNA < 50 copies/mL by Missing = Excluded Approach

The proportion of subjects with HIV-1 RNA < 50 copies/mL will be analyzed using the Missing = Excluded (M = E) for imputing missing HIV-1 RNA values:

In this approach, all missing data will be excluded in the computation of the percentages (ie, missing data points will be excluded from both the numerator and denominator in the computation). The denominator for percentages at a visit is the number of subjects in the All B/F/TAF Analysis Set with non-missing HIV-1 RNA value at that visit.

For M = E analysis, the number and percentage of subjects with HIV-1 RNA in the following categories will be summarized:

- < 50 copies/mL
 - < 20 copies/mL
 - < 20 Not Detectable
 - < 20 Detectable
 - 20 to < 50 copies/mL
- 50 to < 200 copies/mL
- 200 to < 400 copies/mL
- 400 to < 1000 copies/mL
- \geq 1000 copies/mL

The 95% CI of the proportion of subjects with HIV-1 RNA < 50 copies/mL within each subject group will be provided using the Clopper-Pearson Exact method.

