## PROTOCOL SYNOPSIS

**Gilead Sciences, Inc.**  
**[name]**  
**[name]**

---

**Study Title:** A Phase 3, Randomized, Open Label Study to Evaluate the Safety and Efficacy of Switching to a Fixed Dose Combination (FDC) of GS-9883/Emtricitabine/Tenofovir Alafenamide (GS-9883/F/TAF) from Elvitegravir/Cobicistat/Emtricitabine/Tenofovir Alafenamide (E/C/F/TAF), Elvitegravir/Cobicistat/Emtricitabine/Tenofovir Disoproxil Fumarate (E/C/F/TDF) or Atazanavir + Ritonavir + Emtricitabine/Tenofovir Disoproxil Fumarate (ATV+RTV+FTC/TDF) in Virologically Suppressed HIV-1 Infected Women

---

**IND Number:** 125589

**EudraCT Number:** Not Applicable

**Clinical Trials.gov Identifier:** NCT02652624

---

**Study Centers Planned:** Approximately 30 centers in North America  
Approximately 2 centers in Dominican Republic  
Approximately 6 centers in Thailand  
Approximately 20 centers in Russia  
Approximately 1 center in Uganda

---

**Objectives:** The primary objective of this study is:

- To evaluate the efficacy of switching to an FDC of GS-9883/F/TAF versus continuing on a regimen consisting of E/C/F/TAF, E/C/F/TDF or ATV+RTV+FTC/TDF in virologically suppressed HIV-1 infected women as determined by the proportion of subjects with HIV-1 RNA  $\geq$  50 copies/mL at Week 48

The secondary objective of this study is:

- To evaluate the safety and tolerability of the treatment groups through Week 48

---

---

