## 6.5. Treatment Assessments (Post Week 48)

### 6.5.1. Post Week 48 Assessments

At the Week 48 Visit, subjects who completed 48 weeks of study drug treatment and are in a country where GS-9883/F/TAF FDC is not available will be given the option to receive GS-9883/F/TAF FDC for an additional 48 weeks and attend study visits every 12 weeks or until the product becomes accessible to subject through an access program, or until Gilead Sciences elects to discontinue the study in that country, whichever occurs first.

Subjects who continue participation in the study and receive GS-9883/F/TAF will return for study visits every 12 weeks. Study visits are to be completed within  $\pm$  6 days of the protocol-specified visit date unless otherwise specified.

Subjects participating in the study post Week 48 will be required to return for study visits according to the schedule presented in [Appendix 2](#) Study Procedures Table and described in the text below:

- Review of AEs and changes in concomitant medications
- Complete physical examination (**Every 48 weeks**) (urogenital/anorectal exams will be performed at the discretion of the Investigator) or symptom-directed physical examination as needed
- Vital signs measurement (blood pressure, pulse, respiration rate, and temperature), including weight
- 12-lead ECG performed supine (**Every 48 weeks**)
- Urine collection for the following laboratory procedures:
  - Urinalysis
  - Urine albumin, urine creatinine, urine protein, retinol binding protein and beta-2 microglobulin. (**Every 24 weeks**)
  - Urine pregnancy test (females of childbearing potential only); positive urine pregnancy tests will be confirmed with a serum test. If the test is positive, subjects on GS-9883/F/TAF will be discontinued
  - Urine storage sample for possible additional clinical testing
- Blood sample collection for the following laboratory analyses:
  - Chemistry profile: alkaline phosphatase, AST, ALT, GGT, total bilirubin, direct and indirect bilirubin, total protein, albumin, bicarbonate, BUN, calcium, chloride, creatinine, glucose, phosphorus, magnesium, potassium, sodium, uric acid, and amylase (reflex lipase testing is performed in subjects with total amylase  $> 1.5 \times$  ULN) TSH will be analyzed every 24 weeks.

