3.2. Subject Grouping

For the all B/F/TAF analysis including extension phase, subjects will be grouped into the following groups:

- B/F/TAF group: This group includes all subjects who were randomized to B/F/TAF in the randomized phase of this study. All data from both the randomized and extension phases (if applicable) will be included.
- Stay on Baseline Regimen (SBR) to B/F/TAF group: This group includes all subjects who were randomized to continuing pre-existing regimen in the randomized phase of this study, and who then switched to B/F/TAF in the extension phase. Only data collected on and after the extension phase first dose date of B/F/TAF will be included, except that data collected **on or prior to** the extension phase first dose date of B/F/TAF will be used to derive the baseline value for the all B/F/TAF analysis.
- All B/F/TAF group: This group includes all subjects who are in the All B/F/TAF Analysis Set, which combines the two groups above.

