7.2.1. Summaries of Numeric Laboratory Results

Descriptive statistics will be provided by treatment group for each laboratory test specified in the study protocol as follows:

- Baseline values
- Values at each postbaseline analysis window
- Change from baseline at each postbaseline analysis window
- Percentage change from baseline to each postbaseline analysis window (if specified)

A baseline laboratory value will be defined as the last nonmissing value obtained on or prior to the date of first dose of B/F/TAF. Change from baseline to a postbaseline visit will be defined as the postbaseline value minus the baseline value. The mean, median, Q1, Q3, minimum, and maximum values will be displayed to the reported number of digits; SD values will be displayed to the reported number of digits plus 1.

In the case of multiple values in an analysis window, data will be selected for analysis as described in Section 3.8.3.

Calcium Corrected for Albumin

Calcium corrected for albumin will be calculated and summarized for the study. The following formula will be used when both serum calcium and albumin results for a given blood drawn are available and serum albumin value is < 4.0 g/dL.

- Calcium corrected for albumin (mg/dL) = serum calcium (mg/dL) + 0.8 x (4.0 - albumin (g/dL)).

Toxicity grading for calcium will be applied based on the corrected values.

Estimate GFR

The following formulae will be used to calculate eGFR_{CG}:

- eGFR(CG) (mL/min) = [(140 – age (yrs)) × weight (kg) × (0.85 if female)] / (SCr (mg/dL) × 72), where weight is total body mass in kilograms.

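### In the B/F/TAF and All B/F/TAF columns, by-visit summaries and the CD4 plot run across Week 48, where membership changes by design, so a later shift can reflect who is measured

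*SAP*

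**What the plan says.** **Who is followed after Week 48.** SAP 1.2 states that "subjects in a country where B/F/TAF FDC is not available will be given the option to receive B/F/TAF FDC". Protocol 6.5.1 adds a completion condition: the offer goes to "subjects who completed 48 weeks of study drug treatment and are in a country where GS-9883/F/TAF FDC is not available". Entry is voluntary. The extension lasts 48 more weeks at most and can stop sooner, "until the product becomes accessible to subjects through an access program, or until Gilead elects to discontinue the study in that country".

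**How the data are grouped.** For women randomized to B/F/TAF, SAP 3.2 says: "All data from both the randomized and extension phases (if applicable) will be included". For women who switch from their baseline regimen, "Only data collected on and after the extension phase first dose date of B/F/TAF will be included", with baseline reset at that dose. The All B/F/TAF column combines both groups.

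**How the data are shown.** SAP 6.2.1 summarizes observed CD4 change at each visit, leaving out missing values, and says: "The mean and 95% CI of change from baseline in CD4 cell count over time will be plotted using observed data". SAP 6.2.2 divides by the women with an HIV-1 RNA value at that visit. SAP 7.2.1 asks for "Change from baseline at each postbaseline analysis window" for laboratory tests, and 7.2.3 to 7.2.5 and 7.3 give similar by-visit summaries for lipids, liver tests, renal measures, weight and vital signs.

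**What bears on changing membership.** SAP 3.3 has no stratification. The subgroups in 3.4 are by prior regimen, for three renal ratios only. The disposition summary (4.1.2 and Appendix Table 1) counts women who finished the randomized phase and stopped there. Appendix Table 2 prints N in each row. Appendix 5, item 10, hides a group in a figure when n is 5 or fewer. No summary follows the same women on both sides of Week 48.

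**The concern.** Up to Week 48 the B/F/TAF column describes the whole randomized arm still under observation. After Week 48 it describes a subset selected by country, by completion of 48 weeks and by choice. This is not ordinary scattered missing data: the plan itself sets the time and the rule.

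If the women who leave had a different mean change from those who stay, the observed mean moves between Week 48 and the next visit even when no woman's own course changes. On a plot of mean change over time, that movement looks like a late effect of the drug. The final analysis does not repeat the randomized comparison, so for the B/F/TAF arm the visits after Week 48 are the new information on its longer-term course. The by-visit tables and the CD4 plot are where a reader will look for it.

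**Working it through.** The plan states no figure to reproduce here. The check reads the rules together and then works out how large the artefact could be.

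**1. Where the break falls.** From the SAP window tables for the randomized B/F/TAF arm:

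| Measure | SAP table | Last visit with the full arm | Next visit |
|---|---|---|---|
| CD4, HIV-1 RNA, chemistry, eGFR, weight | 3-1 | Week 48 | Week 60 |
| Fasting glucose, lipids | 3-2 | Week 48 | Week 72 |
| Renal ratios | 3-3 | Week 48 | Week 72 |

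**2. The step in the B/F/TAF column.** Let f be the fraction of the arm that continues, c the mean change among continuers and l the mean change among leavers. Suppose the true course is flat after Week 48.

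- Mean at Week 48: f·c + (1 − f)·l
- Mean at the next visit: c
- Apparent step: c − f·c − (1 − f)·l = (1 − f)(c − l) = (1 − f)·d

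Because each woman's change is taken from her own baseline, differences in CD4 level cancel; only a difference d in change matters. For HIV-1 RNA the same formula applies, with proportions below 50 copies/mL in place of means.

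**3. Numbers.** The documents give neither f nor d. Both are assumptions, shown as ranges. The middle value of f, 0.49, is the share of planned centers outside North America: 30 + 2 + 6 + 20 + 1 = 59 and 29/59 = 49.2%. It is a placeholder, not an estimate.

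| f | d = 10 cells/uL | d = 30 | d = 50 |
|---|---|---|---|
| 0.2 | 8 | 24 | 40 |
| 0.49 | 5.1 | 15.3 | 25.5 |
| 0.8 | 2 | 6 | 10 |

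A simulation with 235 women, f = 0.49, d = 30, a flat course and 4,000 runs gave an average step of 15.0 using all available women. Using the same continuers at both visits gave −0.4. Zero holds there by construction. With the simulated within-woman SD of 90, the Monte Carlo standard error is about 90·√2/√115/√4000 = 0.19, so the −0.4 is about two standard errors from zero.

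**4. Scale against the plotted intervals.** With an assumed SD of 150 cells/uL, the 95% half-width is 1.96 × 150/√n: 19.2 at n = 235, 27.4 at n = 115 and 42.9 at n = 47. The 15.3 step in the middle case would lie inside the wider interval after Week 48.

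**5. The pooled column.** For the Table 3-1 measures, switchers have no Week 4 or Week 8 window and join at Week 12; for Table 3-2 they join at Week 24. If the extension is capped at 48 weeks, they have at most about 48 weeks on B/F/TAF. With 235 per arm, the same f in both arms and no other loss, N falls as follows:

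| f | N at Week 48 (235 + 235f) | N after Week 48 (235f) |
|---|---|---|
| 0.2 | 282 | 47 |
| 0.49 | 350 | 115 |
| 0.8 | 423 | 188 |

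With w the switchers' mean change, the step is [(1 − f)(c − l) + f(c − w)]/(1 + f). This column therefore mixes two membership changes. The SBR to B/F/TAF column alone holds only extension entrants, so the randomized-phase exit does not alter it.

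**The case against.** The strongest reply is that no effect is shown. An artefact needs many leavers and a difference in their mean change, and the documents supply neither. If the FDC was unavailable in every country when the Week 48 visits took place, the country rule would select little. The membership change is also visible: N appears in every by-visit row and the disposition table counts those who stop. The analysis is descriptive, with no comparisons. All of this stands. It limits the size of the point but does not answer it: N shows that the group shrank, not whether the mean moved because of it. Voluntary entry and country-by-country endings would still select.

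The remedy has limits too. After Week 48 the B/F/TAF column already consists of women who entered the extension, so the added series is new only in its earlier values. Those values condition on later completion and choice. The cohort can shrink further when a country closes. These are reasons to label the series and print n.

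A reader might infer that about half the arm leaves at Week 48, because the Protocol synopsis plans "Approximately 30 centers in North America" out of 59 (50.8%). The documents do not support that. The figure counts planned centers, not women. SAP 1.2 reports about 57 participating sites with no enrollment limit per site. Neither document says where the FDC was available.

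**Conclusion.** The point holds for the B/F/TAF and All B/F/TAF columns. The SAP joins two phases with different membership rules into one observed-data series and gives no view of the same women across the join. A shift after Week 48 cannot then be separated from a change in who is measured.

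Size and direction are unknown. The range of 2 to 40 cells/uL rests on assumed values of f and d and a flat true course. The pooled counts also assume equal continuation in both arms and the 48-week cap.

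A reader might go further and infer that a Week 60 step is to be expected, or that the trial's efficacy conclusion is affected. The documents support neither. Leavers may have the same mean change as stayers, and lipids and renal ratios have no Week 60 window at all. The primary Week 48 comparison was done in a separate analysis and is not repeated here. This is a cheap improvement to a descriptive analysis.

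**What to change.** In SAP 6.2.1, and in the key by-visit tables of 6.2.2, 7.2 and 7.3, add one descriptive column for women randomized to B/F/TAF who entered the extension. Show the same women from baseline through their last extension visit, with n at each visit. Add the matching line to the CD4 plot and print n beneath it. State that trends after Week 48 are interpreted from this series and not from the pooled All B/F/TAF column. Keep the existing columns.

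The work is small, because the disposition summary already requires extension entry to be identified. If the SAP is already final, SAP 1 provides for recording the change in the study report.

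The costs are more output, wider intervals in a smaller group, a cohort conditioned on completing 48 weeks and choosing to continue, and possible further shrinkage where the extension ends early. If the two series agree up to Week 48, the report can say so, and the concern about that measure is largely met.
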